2. Arrangements for a nursing service to visit the patient’s home for a blood pressure check within the first few days after discharge. *The exact timing of this is not standardized; for example, if the patient is discharged on Friday, the nurse may come 72 hours later on Monday; if the patient is discharged on Thursday, the nurse may come 24 hours later on Friday.*
3. An appointment for a blood pressure check in the clinic where the patient received prenatal care at 7-10 days postpartum; the patient is instructed to bring logs of their twice daily blood pressure measurements to this visit. *Patients with private insurance are told to make this appointment with their prenatal care provider but are not given the*

appointment prior to discharge. Patients who are discharged on or after 7 days postpartum are told to follow up in one week

4. *An appointment for a 6-week postpartum visit. Patients with private insurance are told to make this appointment with their prenatal care provider but are not given the appointment prior to discharge.*

If followed in full by the patient, these policies do follow the current guidelines set forth by ACOG. However, extrapolating from the limited published data regarding follow-up rates and from approximations from our own publicly-insured population, it is reasonable to presume that only about half of these patients present for their one-week blood pressure check appointment.¹⁵ Poor follow-up is not a problem unique to our institution. In a secondary analysis of factors associated with postpartum follow-up and persistent hypertension in women with severe preeclampsia by Levine et al, the 6-week follow-up rate was 52%. Among those with 6-week follow-up, 21% had persistent hypertension.⁴ With low-follow up rates and high rates of persistent hypertension in those that do follow up, clearly there is a large subset of women with continued hypertension who are simply lost to care. Barriers to care in the postpartum period include lack of a consistent provider, lack of understanding of discharge instructions whether due to poor health literacy, a language difference or a failure of the provider to properly explain instructions, and difficulties with transportation. Additionally, many women have difficulty managing their own health issues when also taking care of a newborn, possibly with limited support.¹⁶

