2.2 Specific aims

Our objective is to trial RPM in the postpartum hypertensive population in a randomized control design, with an aim to increase the number of blood pressure measurements taken during the fragile and under-monitored postpartum period and to thereby improve postpartum blood pressure control and reduce severe morbidity and mortality.

Specific Aim 1. To compare the number of blood pressures recorded in the first 10 days postpartum between patients who have been enrolled in an RPM trial to those who are being treated with the usual care. We hypothesize that women using RPM will have more blood pressure values recorded at outpatient blood pressure assessment compared with patients using the usual care.

- **Sub-aim 1: To compare the percentage of elevated blood pressures that are discussed with an obstetric care provider between patients who have been enrolled in an RPM trial to those who are being treated with the usual care.** We hypothesize that women using RPM will communicate more frequently with their providers regarding elevated blood pressure values.
- **Sub-aim 2: To examine the effect of RPM on blood pressure control at 6 weeks in women with HDP.** We hypothesize that more women using RPM will be normotensive, defined as blood pressure < 140/90 mm Hg, at the end of the postpartum period, compared to those randomized to usual care.

Sub-aim 3: To compare time to outpatient initiation or adjustment of antihypertensive medications in women using RPM compared to the usual care. We hypothesize that women using RPM will have shorter time to initiation of medications or shorter time to change in medication regimen in the outpatient setting than those using the usual care.

Specific Aim 2. To compare rates of compliance with follow up visits between patients who have been enrolled in an RPM trial to those who are being treated with the usual care. We hypothesize that women using RPM will have a higher rate of compliance with outpatient blood pressure assessments and postpartum visits than patients using the usual care

- **Sub-aim 1: To analyze factors associated with poor postpartum follow up in both the study group and the control group.** We hypothesize that factors such as socioeconomic status, wait times at the office or clinic where care is provided, number of children at home, and educational level will be associated with lower follow-up rates.

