2.3.6 Outcomes

- 1) **Primary outcome:** Our primary outcome will be percentage of the recommended twice daily blood pressures reported between hospital discharge and outpatient blood pressure assessment.
- 2) **Secondary outcomes:** Secondary outcomes will include:
 1. Percentage of recorded blood pressure values during that time frame that are elevated (>140 systolic OR >90 diastolic)
 2. Percentage of elevated blood pressures that triggered a phone call to an obstetric provider
 3. Rate of attendance at outpatient blood pressure assessment
 4. Incidence of elevated blood pressure at the outpatient blood pressure assessment
 5. Rate of outpatient assessment for postpartum care
 6. Incidence of elevated blood pressure at the postpartum assessment
 7. Time to initiation of antihypertensive medications (in patients who were not on medications at time of discharge) and adjustment of antihypertensive medications
 8. Final dosage of antihypertensive medications at 6 weeks postpartum
 9. Readmission rate
 10. Rate of emergency department visits
 11. Rate of HDP-associated morbidities (e.g.: stroke, seizure, PRES)
 12. Percentage of patients who require a referral to primary care physicians after being discharged from obstetric care at the postpartum visit
 13. Patient satisfaction with the method, to be assessed via a validated clinical survey (attached separately in the document entitled “Surveys”).

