1. **Blood pressures.** For the control group, participants will be asked to provide a record of the blood pressures they are recording at home, and the blood pressures from their office visits will be recorded as well. For the study group, participant blood pressures will be stored in eCC, and the blood pressures from any in-person visits will be recorded as well. Percentage of scheduled blood pressure readings that are recorded will be compared between groups. Incidence of elevated blood pressures during this time will also be compared between groups.
 2. **Communication.** Rate of communication between patient and obstetric provider for each abnormal blood pressure measurement will be compared between groups.
 3. **Adherence.** For both groups, rate of presentation for scheduled appointments will be collected. For the study group, eCC will collect patient reports of reasons why they were unable to check their blood pressure or attend a scheduled appointment
 4. **Time to initiation of medications.** For both groups, time to initiation of anti-hypertensive medications will be tracked
 5. **Final plan at 6 weeks.** For both groups, continuing medication regimens at 6 weeks will be collected. Referral to primary care physician will be collected.
 6. **Hospital readmissions.** Hospital readmission for any indication will be collected for both groups
 7. **ED visits.** Presentation to the emergency department for any indication will be collected for both groups
 8. **Maternal morbidity and mortality.** Incidences of eclampsia, stroke, PRES, maternal death and other preeclampsia-associated morbidities will be collected for both groups
 9. **Home Health Services:** information regarding the use of home health services after discharge including referral to home health services, number of visits and blood pressure at those visits will be collected for both groups

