2.4.2 Statistical analysis

For analysis of discrete (categorical) data in independent samples, the Chi-squared test or Fisher exact probability test will be utilized. For group comparisons, continuous data that satisfy the assumptions of normality and homoscedasticity (homogeneity of variance) will be analyzed by t-test (for 2 independent samples) or analysis of variance (>2 groups, ANOVA) with post hoc comparisons by Scheffe tests. When possible, continuous data that do not fulfill the aforementioned assumptions will be mathematically transformed (e.g., logarithmic transformation) before performing t-tests or ANOVA. In some cases, data that do not satisfy these assumptions will be analyzed by nonparametric methods [Mann-Whitney U Test (for two independent samples) or Kruskal-Wallis One-Way ANOVA (for more than two independent

samples)]. Significant Kruskal-Wallis ANOVAs will be followed by Dunn tests for post hoc analysis. The degree of linear association between variables will be measured by the Pearson product moment correlation coefficient or the Spearman rank-order correlation coefficient and their corresponding tests of significance. Multivariate linear or logistic regression will be utilized where appropriate. In all cases, statistical significance will be assumed when $p < 0.05$. Propensity score analysis will be used as a balancing score as deemed necessary.

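### Visit-based blood pressure and referral outcomes are observed only in attenders, and RPM is expected to change attendance, so an attender-only comparison cannot by itself support sub-aim 2

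*Combined protocol and SAP*

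**What the plan says.** Section 2.3.6 lists, among the secondary outcomes, "Incidence of elevated blood pressure at the outpatient blood pressure assessment" (outcome 4), "Incidence of elevated blood pressure at the postpartum assessment" (outcome 6), "Final dosage of antihypertensive medications at 6 weeks postpartum" (outcome 8) and "Percentage of patients who require a referral to primary care physicians after being discharged from obstetric care at the postpartum visit" (outcome 12). Attendance at each of the two visits is also a secondary outcome (3 and 5).

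Sub-aim 2 of Specific Aim 1 (section 2.2) hypothesises that a larger share of RPM women than usual-care women will be below 140/90 mm Hg at the end of the postpartum period. Specific Aim 2 adds: "We hypothesize that women using RPM will have a higher rate of compliance with outpatient blood pressure assessments and postpartum visits" than women in usual care.

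Section 2.1 presumes that "only about half of these patients present for their one-week blood pressure check appointment". It also cites a study of women with severe preeclampsia in which 52% were followed up at 6 weeks and 21% of those seen were still hypertensive.

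On analysis, section 2.4.2 says: "For analysis of discrete (categorical) data in independent samples, the Chi-squared test or Fisher exact probability test will be utilized". It names no analysis population, no denominator for women who miss a visit, and no missing-data method. Section 2.3.1 ends follow-up at the postpartum visit. For medication, section 2.3.7 says: "For both groups, continuing medication regimens at 6 weeks will be collected", without naming a source for women who do not come.

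**The concern.** Randomisation makes the two whole groups comparable. It does not make the attenders comparable when allocation changes who attends. The plan expects such a change, expects a large share of women to be missing, and says in section 2.1 that many women with continuing hypertension drop out of care. Attendance may therefore be related to blood pressure.

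Sub-aim 2 is a statement about all randomised women. If it is judged on attenders, a difference in blood pressure control can appear when RPM has no effect on blood pressure, in either direction, or a real effect can shrink. Enlarging the sample does not remove this.

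**Working it through.** **The plan's own figure.** The documents give no figure for these outcomes. The stated sample size concerns the primary outcome and reproduces: 60% v 80%, two-sided 5%, 80% power gives 82 per group by the usual normal formula and 81 by the arcsine formula, and 81 × 1.25 = 101.25. It is not in question here.

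**Inputs from the documents.** Control attendance 52% and 21% elevated among attenders (cited study, section 2.1); target enrolment 220 (section 2.4.1), so 110 per arm.

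**Assumptions.** True prevalence p = 30% in both arms, so RPM has no effect on blood pressure; RPM attendance 65% or 80%; odds ratio (OR) of attending, hypertensive v normotensive, of 0.5, 2 or 3. None of these is in the documents.

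**Model.** Let a0 and a1 be the attendance of normotensive and hypertensive women, and m the arm's overall attendance. Solve (1 − p)·a0 + p·a1 = m with a1/(1 − a1) = OR × a0/(1 − a0). The elevated rate among attenders is p·a1/m. Example, controls, OR 2: a0 = 0.4691, a1 = 0.6387, rate = 0.3 × 0.6387/0.52 = 36.8%. Rejection rates use the normal approximation to the two-proportion test with 57 control attenders (0.52 × 110) and about 72 or 88 RPM attenders.

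Same OR in both arms:

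| OR | Control attenders | RPM attenders, 65% attend | Bias, rejection | RPM attenders, 80% attend | Bias, rejection |
|---|---|---|---|---|---|
| 0.5 | 23.1% | 24.8% | +1.7 points, 5.5% | 26.9% | +3.8 points, 7.8% |
| 2 | 36.8% | 34.8% | −2.0 points, 5.7% | 32.6% | −4.2 points, 8.3% |
| 3 | 40.6% | 37.3% | −3.3 points, 6.7% | 33.9% | −6.7 points, 13.2% |

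Bias is RPM minus control; the true difference is zero.

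**Check anchored to the cited 21%.** Suppose the RPM arm consists of the same attenders plus extra ones with assumed prevalence q of 10% to 40%. The RPM rate is (0.52 × 0.21 + (r − 0.52) × q)/r, where r is RPM attendance.
- At r = 0.65: 18.8% to 24.8%, bias −2.2 to +3.8 points.
- At r = 0.80: 17.15% to 27.65%, bias −3.85 to +6.65 points.
- Rejection reaches at most 7.8% and 14.2%.

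The bias is zero in this model if attendance is equal or if q = 21%.

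**Masking.** Take q = 40%, r = 0.80 and an assumed 30% relative reduction. The true difference is −0.3 × (0.1092 + 0.48 × 0.40) = −9.0 points. Attenders show 0.7 × 27.65% − 21% = −1.6 points.

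**Bounds without a model.** Control rate among all randomised: lowest 0.52 × 0.21 = 10.9%; highest 10.9% + 48% = 58.9%. If RPM attendance is 80%, also with 21% elevated, the RPM rate lies between 16.8% and 36.8%. The difference then lies between −42 points (16.8 − 58.9) and +26 points (36.8 − 10.9).

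**Test of a tempting remedy.** Count non-attendance as failure and compare documented control among all 110 per arm. Keep p = 30% in both arms, 80% RPM attendance unrelated to blood pressure, and attendance related to it in controls only. The RPM rate is 0.80 × 0.70 = 56%. The control rate is 0.52 × (1 − attender rate): 40%, 33% and 31% at OR 0.5, 2 and 3. The test rejects about 66%, 94% and 97% of the time although RPM does nothing to blood pressure, because attendance drives the outcome.

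**The case against.** The strongest case on the other side has four parts.

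**The attender-only test is inferred.** Section 2.4.2 is a generic list that also allows regression and, at discretion, propensity scores. That is true. But nothing in it is tied to attendance, and a visit reading has no value for a woman who did not come. The remark in section 2.4.3 that missed visits were allowed for in the sample size concerns numbers at the 7-10 day check, not selection.

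**Other data exist.** RPM women transmit home readings and answer a weekly medication survey, and home-nurse readings are collected in both arms. The plan does not say that any of these replaces a missed visit. The transmitted readings and the survey exist in one arm only, so using them to fill gaps would make ascertainment differ by arm.

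**Outcome 8 is different.** A reader might infer that 6-week medication is also known only for attenders. The documents do not say so: section 2.3.7 collects it for both groups without a condition on attendance. What stands is that the source for non-attenders is not stated.

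**The size can be overstated.** A reader might infer a 7-11 point spurious benefit with 14-26% false rejection. That arises at 80% RPM attendance if hypertensive controls have 2 to 3 times the odds of attending while attendance in the RPM arm is unrelated to blood pressure (36.8% or 40.6% v 30%). Nothing in the documents supports that asymmetry. The 80% in section 2.4.1 is a target for recorded readings, not attendance, and the 52% comes from women with severe preeclampsia. This objection stands and is why the smaller figures are used here.

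**Conclusion.** The concern holds for outcomes 4, 6 and 12, which are tied to a visit that many women are expected to miss and that RPM is expected to make more of them attend. For outcome 8 it is a query about data source.

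An attender-only comparison cannot by itself support sub-aim 2. Under a common attendance odds ratio of 0.5 to 3, the bias is about 2-3 points at 65% RPM attendance and 4-7 points at 80%, with false rejection of about 6-7% and 8-13%. These figures rest on the assumed 30% prevalence, RPM attendance and odds ratios. The 11% to 59% bound needs only the two cited figures, if they apply to this population.

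A reader might infer that the plan will favour RPM. The documents do not support a direction: the sign depends on whether hypertensive women are more or less likely to attend. This is worth correcting before analysis, but it concerns secondary outcomes only.

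**What to change.** In section 2.4.2, for outcomes 4 and 6:
- State that all randomised women are the target population.
- Report, by arm, attendance and blood pressure among attenders side by side, with the attender-only comparison labelled descriptive.
- Give best- and worst-case bounds for non-attenders.
- Prespecify a sensitivity analysis, either multiple imputation or inverse-probability-of-attendance weighting, using the baseline data already collected under section 2.3.7.
- Base the sub-aim 2 conclusion on these analyses of outcome 6.

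Documented control with non-attendance counted as failure may be shown as a supplementary measure of attendance plus control, with both components displayed. It should not be the sub-aim 2 test.

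For outcomes 8 and 12, name one data source used identically in both arms and report the number with data per arm. Do not impute failure: a dosage is not a yes/no success, and a referral has no stated favourable direction.

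The cost is some wording and a small amount of extra analysis, with no new visits. The downside is a less conclusive sub-aim 2, since the bounds will be wide if attendance is near the cited rate, and the imputation or weighting relies on baseline data explaining attendance.

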1. **Blood pressures.** For the control group, participants will be asked to provide a record of the blood pressures they are recording at home, and the blood pressures from their office visits will be recorded as well. For the study group, participant blood pressures will be stored in eCC, and the blood pressures from any in-person visits will be recorded as well. Percentage of scheduled blood pressure readings that are recorded will be compared between groups. Incidence of elevated blood pressures during this time will also be compared between groups.
 2. **Communication.** Rate of communication between patient and obstetric provider for each abnormal blood pressure measurement will be compared between groups.
 3. **Adherence.** For both groups, rate of presentation for scheduled appointments will be collected. For the study group, eCC will collect patient reports of reasons why they were unable to check their blood pressure or attend a scheduled appointment
 4. **Time to initiation of medications.** For both groups, time to initiation of anti-hypertensive medications will be tracked
 5. **Final plan at 6 weeks.** For both groups, continuing medication regimens at 6 weeks will be collected. Referral to primary care physician will be collected.
 6. **Hospital readmissions.** Hospital readmission for any indication will be collected for both groups
 7. **ED visits.** Presentation to the emergency department for any indication will be collected for both groups
 8. **Maternal morbidity and mortality.** Incidences of eclampsia, stroke, PRES, maternal death and other preeclampsia-associated morbidities will be collected for both groups
 9. **Home Health Services:** information regarding the use of home health services after discharge including referral to home health services, number of visits and blood pressure at those visits will be collected for both groups

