2.1 Background

There is a paucity of data on the diagnosis and management of HDP in the postpartum period. The natural history of postpartum HDP is poorly understood, and estimates of the prevalence of the disease vary widely, ranging from 0.3 to 27.5%.⁷ In older studies of patients who had planned postpartum inpatient stays of 1 week or longer, 12% of previously normotensive women became hypertensive and >50% of women with HDP had a systolic/diastolic BP \geq 150/100 mmHg.^{8,9} Since those studies were performed, the length of a hospital admission for delivery has shortened. Most women are now discharged within 48-72 hours of delivery, and many are not evaluated again until their traditional 6-week postpartum visit. However, nearly 20% of women who deliver a baby in the United States will be seen and discharged from an emergency department prior to their traditional 6-week postpartum visit, and an additional 1-2% of patients will be admitted.¹⁰ In a 2016 study, hypertension was found to be the second most common cause of postpartum readmission in the United States, after infection.¹¹ Short-term complications that are known to occur secondary to uncontrolled HDP include stroke, seizure, pulmonary edema, posterior reversible encephalopathy syndrome, renal or hepatic dysfunction, and death.¹² HDP is also a risk factor for the long-term development of cardiovascular disease, hypertension, stroke and renal disease.¹³ Given all of these associated short- and long-term morbidities, close follow up of women with HDP is essential in the postpartum period and beyond. Yet due to the scarceness of empiric data on postpartum BP, there are limited recommendations regarding the initiation, frequency, and duration of postpartum BP monitoring in women with HDP.¹⁴

ACOG guidelines recommend that in women with HDP, blood pressure should be monitored in the hospital or with equivalent outpatient surveillance for at least 72 hours postpartum and again 7-10 days after delivery, or earlier in women with symptoms.¹ At CUIMC, the usual care for discharge of patients with HDP at CUIMC involves the following (hereafter referred to as “usual care”):

1. A prescription for a blood pressure cuff and instructions to measure blood pressures twice daily at home. *No make or model is specified, and the patient is responsible for obtaining the device from a pharmacy.*

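### Section 2.3.7 item 1 lets emergency and readmission pressures count in the RPM arm but not in controls, then compares the incidence of elevated pressure between arms

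*Combined protocol and SAP*

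**What the plan says.** Section 2.3.7, in the list of data collected throughout the study period, treats the arms in separate sentences of item 1. Controls supply their home record, and "the blood pressures from their office visits will be recorded as well". For the RPM group the home readings sit in the eCC software, and "the blood pressures from any in-person visits will be recorded as well". The item ends: "Incidence of elevated blood pressures during this time will also be compared between groups".

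Three other items of that list bear on the point:

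- Item 9, on home health services: "number of visits and blood pressure at those visits will be collected for both groups".
- Item 7: "Presentation to the emergency department for any indication will be collected for both groups".
- Item 6: "Hospital readmission for any indication will be collected for both groups".

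Item 9 names pressures. Items 6 and 7 name only the event.

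In section 2.3.6, secondary outcome 1 is defined as "Percentage of recorded blood pressure values during that time frame that are elevated (>140 systolic OR >90 diastolic"), the time frame being hospital discharge to the outpatient blood pressure assessment. The plan does not say whether in-person values belong to it. Nor does it define the unit (reading or woman), the eligible sources or the exact window of the item 1 comparison.

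**The concern.** A between-arm comparison of elevated pressure needs the same opportunities for a reading to be counted in each arm. Here the RPM arm has a wider in-person source. The additional encounters are ones at which pressure may well be high, and the intervention may generate some of them. Under section 2.3.1 a high flag or a flagged symptom answer leads to telephone contact with the patient and her provider.

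If the text is followed literally, the RPM arm could show more elevated pressure partly because more places were searched for it. This is separate from the difference in how home readings are captured, which is automatic transmission in one arm and a patient-kept log in the other.

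**Working it through.** The plan gives no figure for this comparison. The sample size in section 2.4.1 concerns the primary outcome and plays no part here.

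**1. Sources side by side (section 2.3.7).**

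| Setting | RPM arm | Control arm |
|---|---|---|
| Office visits, scheduled or not | item 1 | item 1 |
| Home-health visits | item 9 | item 9 |
| Emergency visits | event (item 7); pressures fall within item 1's wording | event only (item 7) |
| Readmissions | event (item 6); pressures fall within item 1's wording | event only (item 6) |

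Only the last two rows differ, together with any other non-office encounter.

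**2. Which comparisons are exposed.**
- The primary outcome counts the recommended twice-daily readings, so in-person values are not part of its wording.
- Secondary outcomes 4 and 6 are each tied to one named visit, the same in both arms.
- The item 1 incidence comparison is tied to no visit and is exposed.
- Secondary outcome 1 is exposed only if in-person values count as recorded.

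**3. Direction.** If the unit is the woman with any elevated reading, extra readings can only raise the RPM figure or leave it unchanged. If the unit is the reading, the percentage rises only when the extra readings are elevated more often than home readings.

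**4. Illustrative size.** The documents give neither the rate of non-office encounters in this population nor the share of pressures elevated there. Assumed inputs:
- Home readings per woman: n = 2 × days × 0.8, over 5 to 7 days (0.8 is the plan's target for the RPM arm, section 2.4.1).
- Share of home readings elevated: p = 0.30.
- Share of RPM women with a non-office encounter: s = 0.05 to 0.20.
- Readings per encounter: k = 1 to 6.
- Share of those readings elevated: e = 0.6 to 0.9.

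Reading level: shift = (n·p + s·k·e)/(n + s·k) − p.
- Low (7 days, n = 11.2, s = 0.05, k = 1, e = 0.6): (3.36 + 0.03)/11.25 − 0.30 = 0.0013, or 0.1 points.
- High (5 days, n = 8, s = 0.20, k = 6, e = 0.9): (2.40 + 1.08)/9.2 − 0.30 = 0.0783, or 7.8 points.
- With e = 0.30, the same as at home, the shift is 0.

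Patient level, assuming 50% of women already have an elevated reading, independently of the encounter: shift = 0.5 × s × [1 − (1 − e)^k].
- Low (s = 0.05, k = 1, e = 0.6): 0.5 × 0.05 × 0.6 = 0.015, or 1.5 points.
- High (s = 0.20, k = 6, e = 0.9): 0.5 × 0.20 × (1 − 0.1^6) ≈ 0.100, or 10 points.
- With e = 0.30: from 0.5 × 0.05 × 0.3 = 0.0075 (0.8 points) to 0.5 × 0.20 × (1 − 0.7^6) = 0.088 (8.8 points).

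Independence makes the patient-level figures generous. A woman with a high pressure at an emergency visit is more likely than average to have had a high reading at home.

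**The case against.** The strongest reply is that this is loose drafting. For RPM women, in-person is the natural contrast to remote, and item 1 mentions neither emergency visits nor readmissions. That may be what was meant, but no other section makes the sources equal for those encounters, and an abstractor following the text would treat the arms differently. The objection lowers the weight of the point without removing it.

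A second reply is that section 2.3.1 has total and elevated counts ascertained for each group at the 7-10 day visit, in the context of the home log. This supports reading secondary outcome 1 as home readings only, and if that is intended the outcome is safe. The plan does not say so.

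A third reply concerns size, and much of it stands. A reader might take the Background figure, "nearly 20% of women who deliver a baby in the United States will be seen and discharged from an emergency department" before the 6-week visit, and apply it to 110 women per arm (half of 220): 0.20 × 110 = 22 women. If half or a quarter of them were newly counted as elevated, the RPM arm would gain 22 × 0.5/110 = 10 or 22 × 0.25/110 = 5 points. The documents do not support that estimate. The figure covers all US deliveries and visits for any reason over about six weeks, and the newly counted share is assumed. Women sent in by a high-pressure alert would mostly have an elevated reading in eCC already, and so add nothing at patient level.

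For secondary outcome 1 the effect can be small. Assume 110 women × 14 readings × 0.8 = 1,232 readings, 30% elevated (369.6), and one reading per emergency visit. Adding 22 readings, all elevated, gives 391.6/1,254 = 31.2%. If the visits spread evenly over 42 days, about 22 × 7/42 ≈ 4 fall in the first week, giving 373.6/1,236 = 30.2%.

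**Conclusion.** The point holds as a limited one. Item 1 makes the in-person source depend on the arm, and the part that no other item equalises is pressure at emergency, readmission or other non-office encounters. It affects the item 1 incidence comparison and, conditionally, secondary outcome 1. The direction is probably upward in the RPM arm. At reading level this requires the extra encounters to have a higher elevated share than home readings, which is plausible but not shown. The ranges above illustrate the mechanism on assumed inputs and do not estimate the bias.

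Two stronger readings should be resisted:

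- A reader might infer that control in-person pressures come solely from office visits. Item 9 collects home-health pressures in both arms, and an unscheduled office visit is still an office visit.
- A reader might infer that a real benefit on blood pressure control could be hidden. The plan's own control measure, in sub-aim 2 of Specific Aim 1, is pressure below 140/90 mm Hg at the end of the postpartum period. It corresponds to secondary outcome 6, which is read at one named visit in both arms and is not touched.

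**What to change.** Replace the two arm-specific phrases in section 2.3.7 item 1 with one sentence for both arms. For example, in-person pressures entering the between-arm comparison come from office visits in each arm, home-health pressures are handled the same way in each, and pressures from emergency visits and readmissions are left out in both.

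In the same place, state whether secondary outcome 1 and the item 1 incidence use home readings alone or also in-person readings, whether the unit is the reading or the woman, and the time window.

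The cost is a few lines of text and no new data. The small downside is that some in-person readings in the RPM arm go unused in this comparison. Widening the control source to match the RPM arm would also restore symmetry, but it would mean collecting emergency and readmission pressures in controls, which items 6 and 7 do not provide for. Home-health pressures need not be excluded, since they are already collected alike in both arms.
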